7.1.2. Serious Adverse Event

A serious adverse event is any untoward medical occurrence that, at any dose:

1. Results in death;

2. Is life-threatening;

NOTE: The term “life-threatening” in the definition of “serious” refers to an event in which the study participant was at risk of death at the time of the event. It does not refer to an event, which hypothetically might have caused death, if it were more severe. For example, drug-induced hepatitis that resolved without evidence of hepatic failure would not be considered life-threatening even though drug-induced hepatitis can be fatal.

3. Requires hospitalization or prolongation of existing hospitalization;

NOTE: In general, hospitalization signifies that the patient has been detained at the hospital or emergency ward for observation and/or treatment that would not have been appropriate in the physician’s office or out-patient setting. Complications that occur during hospitalization are adverse events. If a complication prolongs hospitalization or fulfills any other serious criteria, the event is serious. When in doubt as to whether “hospitalization” occurred or was necessary, the adverse event should be considered serious. Hospitalization for elective treatment of a pre-existing condition that did not worsen from the Week 24/Baseline visit is not considered an adverse event.

4. Results in persistent or significant disability/incapacity;

NOTE: The term disability means a substantial disruption of a person’s ability to conduct normal life functions. This definition is not intended to include experiences of relatively minor medical significance such as uncomplicated headache, nausea, vomiting, diarrhea, influenza, and accidental trauma (eg, sprained ankle), which may interfere or prevent everyday life functions but do not constitute a substantial disruption.

5. Is a congenital anomaly/birth defect;

6. Important medical events that jeopardize the patient and may require medical or surgical intervention to prevent one of the outcomes listed above. Examples of such events are invasive or malignant cancers, intensive treatment in an emergency room or at home for allergic bronchospasm, blood dyscrasias or convulsions that do not result in hospitalization, or development of drug dependency or drug abuse.

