7.1. Adverse Event Definitions

7.1.1. Adverse Event

Adverse event: An adverse event is any unfavorable and unintended sign (including an abnormal laboratory finding), symptom, or disease (new or exacerbated) temporally associated with the use of a medicinal product, whether or not related to the medicinal product.

Events meeting the definition of an adverse event **include**:

- A worsening, excluding minor fluctuations, in the nature, severity, frequency, or duration of a pre-existing condition;
- Development of an intercurrent illness during the study;
- Development of symptoms that may or may not be related to the use of a concomitant medication or investigational product;
- Injury or accidents: If a medical condition is known to have caused the injury or accident, the medical condition and the accident should be reported as 2 separate medical events (eg, for a fall secondary to dizziness, both “dizziness” and “fall” should be recorded separately); and
- An investigational abnormality (eg, laboratory parameter, vital sign, ECG) only if the abnormality is considered clinically significant by the investigator based on at least one of the following criteria:
 - Induces clinical signs or symptoms;
 - Requires active intervention;
 - Requires interruption or discontinuation of study drug.

Events that **do not** meet the definition of an adverse event include:

- Medical or surgical procedures (eg, surgery, endoscopy, tooth extraction, transfusion); the condition that leads to the procedure is an adverse event;
- Pre-existing diseases or conditions present or detected before the start of study drug administration that do not worsen;
- Situations where an untoward medical event has not occurred (eg, planned hospitalization for an elective procedure, with elective defined as known or planned at the time of signing of the informed consent);
- Events of heavy menstrual bleeding, as heavy menstrual bleeding is quantified as an efficacy endpoint, unless meets seriousness criteria.

Adverse events that occur during the study should be evaluated by the investigator and graded according to Common Terminology Criteria for Adverse Events (CTCAE). Episodic adverse

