9.5. Safety Analyses

Safety assessments will include treatment-emergent adverse events, vital signs, physical examinations, clinical laboratory tests, and 12-lead ECGs.

The treatment-emergent period will be defined as the period of time from the first dose date of study drug in the parent study through approximately 30 days after the last dose of study drug, or the date of initiation of another investigational agent or hormonal therapy affecting the hypothalamic-pituitary-gonadal axis or surgical intervention for uterine fibroids, whichever occurs first. Safety will be assessed through summaries of adverse events, the frequency of treatment discontinuations due to adverse events, laboratory evaluations, and bone densitometry results.

The severity of all adverse events is to be evaluated by the investigator based on the National Cancer Institute's CTCAE. All adverse events will be coded to preferred term and system organ class using MedDRA 20.0 or higher. The incidence of adverse events will be presented by MedDRA system organ class and preferred term, relationship to study drug treatment, and severity. A patient reporting the same adverse event more than once is counted once, and at the maximum severity or strongest relationship to study drug treatment when calculating incidence.

Laboratory data consist of chemistry, hematology, and hormonal tests. Only data collected by the central laboratory will be used to do the analyses. The National Cancer Institute CTCAE, will be used to categorize toxicity grade for the laboratory parameters. Shift tables will be provided for each gradable parameter to summarize baseline toxicity grade versus post-baseline toxicity grade. For laboratory parameters that are not gradable by the CTCAE, a shift table based upon the normal range (low, normal, and high) will be provided for each parameter to summarize the parent study Baseline versus post-baseline results. All data will be listed and summarized by visit. The change from parent study Baseline to each post-baseline study visit will be presented by parent study treatment group for each laboratory test.

For vital signs parameters, including temperature, all data will be listed and summarized by visit. The change from parent study Baseline to each post-baseline study visit will be presented by parent study treatment group for each parameter.

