9.1. Adverse Events

Adverse events will be collected from the time of the first dose of open-label study drug through the safety follow up visit approximately 30 days after the last dose of open-label study drug (the end of extension treatment period), or the date of initiation of another investigational agent or hormonal therapy or surgical intervention or entering the MVT-601-035 study, whichever occurs first. Serious adverse events reported to the investigator after the safety reporting period should be reported to the sponsor if the investigator assesses the event as related to study drug.

The severity of all treatment-emergent adverse events will be evaluated by the investigator based on the National Cancer Institute's Common Terminology Criteria for Adverse Events (CTCAE) and will be coded to preferred term and system organ class using MedDRA 22.0 or higher.

A treatment-emergent adverse event is defined as any adverse event that occurs after administration of the first dose of parent study drug.

Adverse event summaries will be based on treatment-emergent adverse events in the parent and extension studies, unless otherwise specified. All adverse events in the parent and extension studies will be listed in by-patient listings.

The following tabular summaries that include the number and percentage of patients will be provided:

- Overview of adverse events;
- All adverse events;
 - By SOC and PT;
 - By decreasing frequency of PT;
 - By SOC, PT, and maximum severity;
 - Study drug-related per investigator by SOC and PT;
 - By time to onset, SOC and PT;
- Grade 3 or above adverse events;
 - By SOC and PT;
 - By decreasing frequency of PT;
 - Study drug-related per investigator by SOC and PT;
- Grade 2 or above adverse events;
 - By SOC and PT;
 - By decreasing frequency of PT;
 - By SOC, PT, and maximum severity;

- Study drug-related per investigator by SOC and PT;
- Adverse events leading to study drug withdrawal;
 - By SOC and PT;
 - By decreasing frequency of PT;
- Adverse events leading to dose interruption;
 - By SOC and PT;
 - By decreasing frequency of PT;
- Adverse events resulting in fatal outcome;
 - By decreasing frequency of PT;
- Serious adverse events;
 - By SOC and PT;
 - By decreasing frequency of PT;
 - By SOC, PT, and maximum severity;
 - By SOC, PT, and relationship to study drug;
- Adverse events of clinical interest (ALT or AST $\geq 3 \times$ ULN);
 - By SOC, PT, and maximum severity;
 - By decreasing frequency of PT.

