9.1.3. Serious Adverse Event

Serious adverse events throughout the parent and extension studies will be summarized by SOC, PT, and/or maximum severity, relationship to study treatment.

The data handling conventions for and the definition of a serious adverse event are discussed in this section. All deaths during the studies, including the post treatment follow-up period, and deaths that resulted from a process that began during the studies, should be included in the analysis. For more details, deaths occurring during the following time periods or under the following conditions should be considered:

- Deaths occurring during participation in either the parent study or study MVT-601-3003;
- Deaths occurring after a patient leaves a study, or otherwise discontinues study drug, whether or not the patient completes the study to the nominal endpoint, if the death:
 - Is the result of a process initiated during the study or other drug exposure, regardless of when it actually occurs; or
 - Occurs within a time period that might reflect drug toxicity for a patient leaving a study or otherwise discontinuing drug.

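### The note on elective admissions in Protocol 7.1.2 measures worsening from Week 24, but the serious-event tables start at the first parent-study dose, so a serious classification can be lost

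*Protocol*

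**What the plan says.** The note under the hospitalization criterion in Protocol 7.1.2 reads: "Hospitalization for elective treatment of a pre-existing condition that did not worsen from the Week 24/Baseline visit is not considered an adverse event".

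Two items in the Protocol 7.1.1 list of things that are not adverse events bear on it. One is "Pre-existing diseases or conditions present or detected before the start of study drug administration that do not worsen", which does not say whether parent or extension drug is meant. The other gives as its example a "planned hospitalization for an elective procedure, with elective defined as known or planned at the time of signing of the informed consent", which does not say which consent is meant.

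The analysis uses an earlier starting point. Protocol 9.5: "The treatment-emergent period will be defined as the period of time from the first dose date of study drug in the parent study". SAP 9.1: "A treatment-emergent adverse event is defined as any adverse event that occurs after administration of the first dose of parent study drug". SAP 9.1.3 sets the scope of the serious-event tables: "Serious adverse events throughout the parent and extension studies will be summarized by SOC, PT, and/or maximum severity, relationship to study treatment".

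Two further provisions limit the effect. Protocol 7.1.1 treats the condition behind a medical or surgical procedure as an adverse event. The adverse-event footnote to the Schedule of Activities (Protocol 1.1) assigns events with onset before the first extension dose to the parent study. It refers sites to the Study Reference Manual for recording those still ongoing; that manual is not among the documents.

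**The concern.** The note and the tables it feeds use reference dates 24 weeks apart. A site applying the note asks only whether the condition has worsened since Week 24. The 52-week tables ask what has happened since the first parent-study dose. A condition that emerged or worsened on parent-study treatment, then held steady, passes the site's test as unchanged although it is treatment-emergent for the analysis.

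If such a condition leads to an elective admission during the extension, the admission would ordinarily make the event serious, and the note removes that. Long-term safety, including adverse events, is a stated objective of the study, and the serious-event table is one of its main outputs.

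**Working it through.** The plan gives no figure on this point to reproduce. The check sets the passages side by side and asks which admissions the note reaches.

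**Step 1: which conditions.** Week 24 in the note attaches to worsening. The note does not define pre-existing, and 7.1.1 leaves the relevant study drug open. Both readings therefore have to be tried:

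| Course of the condition | Pre-existing = before extension drug | Pre-existing = before parent drug |
|---|---|---|
| Present before the parent dose, never worsened | Exempt, as intended | Exempt, as intended |
| Present before the parent dose, worsened in Weeks 0-24, stable since | Exempt | Exempt |
| First arose in Weeks 0-24, stable since Week 24 | Exempt | Not reached by the note |
| Worsened after Week 24 | Not exempt | Not exempt |

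The second row is exempt under either reading, although 7.1.1 itself lists worsening of a pre-existing condition as an adverse event. Settling the meaning of pre-existing alone therefore does not close the gap; the reference date for worsening has to move as well.

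**Step 2: which admissions.** Under 7.1.1, elective is limited to what was known or planned at consent. The consent this protocol governs is the extension consent, which the Schedule of Activities allows at the Week 24/Baseline visit or up to 30 days before it. An admission arranged late in the parent study for a condition that emerged on treatment can therefore qualify. If the parent-study consent were the reference, no admission could already have been planned for a condition that first arose after the first parent dose. The note in 7.1.2 neither repeats nor cross-refers to this definition, so a site using the everyday sense of elective would exempt more.

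**Step 3: what is lost.** A condition with onset in Weeks 0-24 is reported in the parent study, and the SAP 9.1 summaries include parent-study events, so it remains in the 52-week tables. Only the serious classification is at risk.

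**Step 4: whether another passage repairs it.** The instruction in 7.1.2 to lean towards serious in case of doubt concerns only whether hospitalization occurred or was necessary. SAP 9.1.3 announces the definition and data-handling conventions for serious events, then gives conventions only for deaths. Nothing in the two documents says that a parent-study event leading to an extension admission becomes serious.

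**Step 5: size per event.** The documents give about 600 patients and three parent-study groups, but no group sizes and no rate of elective hospitalization. Assuming equal groups, 600/3 = 200 and 1/200 = 0.5 percentage points per event. If a group held 150 or 250 women (also assumed), the figure would be 1/150 = 0.67 or 1/250 = 0.40 points.

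**The case against.** The strongest defence is that the two rules do different jobs. Protocol 7.2.1 collects events under this protocol only from the first extension dose, and earlier onsets belong to the parent study. A Week 24 reference for sites collecting extension events fits that split, while Protocol 9.5 and SAP 9.1 govern how the two datasets are pooled. This explains how the wording may have come about. It does not reconcile it, because the pooled tables depend on the serious classification as the sites make it, and no rule adjusts that classification at pooling.

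The limits on reach also stand. The condition must be unresolved, stable since Week 24, treated electively in hospital and, under 7.1.1, already planned at consent. Women expected to have gynecological surgery or ablation for fibroids are excluded by inclusion criterion 3, and Protocol 5.9.3 bars fibroid interventions unless urgently needed for safety.

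A reader might infer stronger conclusions that the documents do not support:

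- **That Week 24 defines pre-existing.** It qualifies worsening only; the meaning of pre-existing is left open.
- **That such hospitalizations are never collected.** Protocol 7.2 requires events to be followed until they resolve, stabilize or become chronic. The Study Reference Manual may also tell sites how to update ongoing parent-study events.
- **That the rule covers 46% of conditions.** 24/52 = 0.46 is a share of treatment time. It is not a share of conditions or admissions.
- **That the groups are demonstrably affected unequally.** Groups A and B took relugolix in Weeks 0-24 and Group C took placebo, so the excluded conditions would have arisen on different treatments. No rate is given from which a difference could be estimated, and no formal treatment comparisons are planned.

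**Conclusion.** The inconsistency is real, and the two documents do not resolve it. Followed literally, the note can remove the serious classification from an elective extension admission for a condition that arose or worsened in Weeks 0-24. Serious-event incidence over 52 weeks may therefore be understated; it is not shown to be.

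The number of events cannot be derived and is probably small, given how many conditions must coincide. Each would move a group's incidence by about 0.5 percentage points under the assumed 200 per group. The conclusion assumes that sites apply the note as written and that the unseen manual does not override it. The wording should be corrected because the ambiguity affects a stated safety objective and costs little to remove.

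**What to change.** 1. In Protocol 7.1.2, change the reference for worsening from the Week 24/Baseline visit to parent study Baseline, and limit pre-existing to conditions present before the first dose of parent-study drug.
2. In Protocol 7.1.1, name the parent-study informed consent as the reference for elective.
3. State in the protocol, and repeat in SAP 9.1.3, that an event with onset in the parent study that leads to hospitalization in the extension counts as serious in the 52-week tables. This would apply to all three groups, placebo included, in line with a treatment-emergent definition that runs from the first dose of any parent-study drug.

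These changes concern event classification and reporting only. The cost is revised wording, a few additional serious-event reports, and follow-up updates to some parent-study event records.

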7.2. Adverse Event Reporting

The reporting of serious adverse events by the sponsor (Myovant Sciences GmbH) to regulatory authorities is a requirement and each authority has a timetable for reporting these events based

upon established criteria. Likewise, it is the responsibility of the investigator to report serious adverse events to their local institutional review board (IRB) or institutional ethics committee (IEC).

Care will be taken not to introduce bias when detecting adverse events and/or serious adverse events. Open-ended and non-leading verbal questioning of the patient is the preferred method to inquire about adverse event occurrence. Appropriate questions include:

- “How are you feeling?”
- “Have you had any (other) medical problems since your last visit/contact?”
- “Have you taken any new medicines, other than those provided in this study, since your last visit/contact?”

The patient’s answers to study questionnaires will not be used as a primary means to collect adverse events, however they should be reviewed by the study site personnel and the study monitors. Should the investigator or site staff become aware of a potential adverse event through the information collected with these instruments, proper follow-up with the patient for medical evaluation should be undertaken. Through this follow-up, if it is determined that an adverse event not previously reported has been identified, normal reporting requirements should be applied.

All patients who experience an adverse event will be evaluated at appropriate time intervals until the event resolves or has stabilized or become chronic. At the conclusion of the study, the investigator and medical monitor will assess unresolved adverse events and determine if additional follow-up is warranted.

All adverse events, whether or not related to the study drug treatment, must be fully and completely documented on the adverse event case report form and in the patient’s source documents. In addition, any adverse event resulting in permanent treatment discontinuation must be recorded on the appropriate case report form as well as documented in the patient’s source documents. Adverse event terms should include a diagnosis, as available, in preference to listing the individual signs and symptoms. If the diagnosis is not known, the investigator should record each sign and symptom as an individual adverse event.

Overdose and pregnancy in the patient will be reported as described in Section 7.7 and Section 7.8, respectively.

7.2.1. Adverse Event Reporting Period

Adverse events and serious adverse events will be collected under this extension study protocol from the administration of the first dose of extension study drug until the Follow-up visit approximately 30 days after the last dose of study drug or the date of initiation of another investigational agent or hormonal therapy affecting the hypothalamic-pituitary-gonadal axis or surgical intervention for uterine fibroids, whichever occurs first, as also specified in the study Schedule of Activities (Section 1.1). Serious adverse events reported to the investigator after the safety reporting period should be reported to the sponsor if the investigator assesses the event as related to the study drug treatment.

Reporting instructions for serious adverse events are provided in Section 7.6.

7.3. Assigning Causal Relationship to Study Drug

The reasonable possibility of the relationship of an adverse event to study drug(s) is to be assessed with careful medical consideration at the time of evaluation of an adverse event. The following definitions are to be used for the relationship of the adverse event to study drug:

- **Probably related:** A clinical event, including laboratory test abnormality, with a reasonable time sequence to administration of the drug, unlikely attributed to concurrent disease or other drugs or chemicals, and that follows a clinically reasonable response on readministration (rechallenge) or withdrawal (dechallenge).
- **Possibly related:** A clinical event, including laboratory test abnormality, with a reasonable time sequence to administration of the drug but that could also be explained by concurrent disease or other drugs or chemicals. Information on drug withdrawal may be lacking or unclear.
- **Not related:** A clinical event, including laboratory test abnormality, with a temporal relationship to drug administration that makes a causal relationship improbable and/or in which other drugs, chemicals, or underlying disease provide a plausible explanation.

All adverse events, whether or not related to study drug, must be fully and completely documented on the adverse event page of the eCRF and in the patient's clinical record. In the event a patient is withdrawn from the study because of an adverse event, it must be recorded on the eCRF as such.

